#### **5.4.7 Concomitant treatment**

The investigator should instruct the patient to notify the study site about any new medications he/she takes after the patient was enrolled into the study.

#### **5.4.8 Prohibited Treatment**

Use of the following treatments is NOT allowed concomitantly with the study drug during the course of the study: (use can only be considered if the study drug is permanently discontinued):

- Immunosuppressive medication (e.g. cyclosporine, azathioprine, methotrexate, cyclophosphamide, mitoxantrone, cladribine);
- Other concomitant medications: immunoglobulins, monoclonal antibodies (including natalizumab), INF- $\beta$ , glatiramer acetate, adrenocorticotropic hormone (ACTH). The administration of any live or live attenuated vaccines (including for measles) is prohibited while patients are receiving study drug and for 3 months after study drug discontinuation. They may be administered, thereafter, once there is confirmation that lymphocyte counts are in the laboratory normal range. Use of the following treatments is allowed to manage potential adverse reactions associated with the study drug:
  - i. anticholinergics (atropine s.c. or i.v.) for treatment of symptomatic bradycardia as the first line treatment, up to 3 mg/day;
  - ii. beta-agonists/sympathomimetics (dopamine drip 5-20 $\mu$ g/kg/min or epinephrine drip 2- 10  $\mu$ g/min) for treatment of non-responsive bradycardia. Standard short course of corticosteroids (methylprednisolone i.v.) is allowed for treatment of relapses.

The medications allowed for treatment of adverse reactions and relapses are not considered study supplies, and therefore, need to be supplied by the study site. The investigator should instruct the patient to notify the study site about any new medications he/she takes after the start of the study drug.

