### **4.1 Inclusion criteria**

1. Written informed consent must be obtained before any assessment is performed.
2. RRMS patients aged between 18-65 years that fulfill following criteria:
  - d) In non-treated/newly-diagnosed patients with two or more serious attacks within one year or three or more serious attacks within two years and one or multiple gadolinium-enhancing lesions in cranial MRI or with significantly increased T2 lesions compared to the previous MRI.
  - e) In non-responders despite treatment with a beta-interferon or glatiramer acetate with adequate duration and dose, where:
    - a. adequate treatment duration is at least 1 year and,
    - b. non-responders are patients with no changes in attacks or increased number of attacks after one year of treatment, or with more severe attacks, or those with one or multiple contrast enhancing lesions in cranial MRI or where there is an increase in T2 lesions identified with successive MRI's.
  - f) In RRMS patients who are unable to tolerate first-line treatments due to adverse effects associated with parenteral administration.
3. Last relapse of the patient should be at least 2 months before study entry.
4. Last steroid dose of the patient should be at least 1 month before study entry.

5. Last interferon or glatiramer acetate dose of the patient should be at least 1 month before study entry.
6. Last cyclophosphamide, mitoxantrone, teriflunamide, natalizumab and azathioprine dose of the patient should be at least 3 months before study entry.

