## **5 Treatment**

### **5.1 Protocol requested treatment**

#### **5.1.1 Investigational treatment**

Treatment will be 0.5 mg p.o fingolimod daily for the treatment arm. The study drug will be provided by Novartis .

Control group will not receive any treatment.

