#### **5.1.2 Additional study treatment**

No additional treatment beyond investigational treatment is requested for this trial.

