## 5.4.5 Permitted dose adjustments and interruptions of study treatment

Dose adjustments will not be allowed, however drug interruptions will be allowed based on

Conditions/events that may lead to the study drug interruptions based on investigator judgment and overall clinical assessment:

- reported serious adverse event;
- emergency medical condition, unplanned hospitalization, involving use of excluded concomitant medications;
- abnormal laboratory value(s) or abnormal test or examination result(s) (e.g. PFT, liver function tests, ophthalmic findings etc.).
- patient's non-compliance.

Should the patient interrupt the study drug, and should the investigator decide in agreement with the sponsor to re-initiate treatment with the study drug, depending on the duration of the interruption (see below), the first dose at re-start may need to take place under supervision of the First Dose Administrator in a similar manner as the first intake of the study medication. It is recommended not to initiate beta-blockers, calcium-channel blockers or digoxin treatment within one week before or after the day of re-initiation of the study drug administration due to a possible additive effect on heart rate reduction.

When re-starting of study drug monitoring (as for first dose) is mandatory in the following cases:

- The treatment lasted for less than 8 days and was interrupted for more than 1 day
- The treatment lasted for 8 days or more and was interrupted for 8 days or more

Re-start decision should be made on a case by case basis and should be discussed with the Medical Advisor at Novartis. A reason for the interruption of treatment and time of interruption should be appropriately documented in the source documents as well as in the Dosage Administration Record CRF. All required guidelines for the above matters are given as an appendix to this protocol

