#### **5.4.9 Discontinuation of study treatment and premature patient withdrawal**

Patients may voluntarily withdraw from the study for any reason at any time. They may be considered withdrawn if they state an intention to withdraw, fail to return for visits, or become lost to follow-up for any other reason.

If premature withdrawal occurs for any reason, the investigator must make every effort to determine the primary reason for a patient's premature withdrawal from the study and record this information on the Study Completion CRF.

The investigator should discontinue study treatment for a given patient or withdraw the patient from study if, on balance, he/she believes that continuation would be detrimental to the patient's well-being.

Study drug must be discontinued for a given patient if the investigator determines that continuing it would result in a significant risk for that patient. The following conditions/events may be considered sufficient to support a decision about the study drug discontinuation in individual cases:

- serious adverse event (e.g. cardiac failure, diagnosed malignancy)
- abnormal laboratory value(s) including liver function tests or abnormal test result(s) (e.g. PFTs, MRI and ophthalmic findings). See below and Appendix 7 and 8 for guidance for safety monitoring
- withdrawal of consent (e.g., in case the patient does not consent to continue in the study after a confirmed relapse or disability progression)
- pregnancy
- use of prohibited medications, listed in Section 5.1 and 6.6.5
- adverse events
- protocol violation
- unsatisfactory therapeutic effect
- patient's condition no longer requires study treatment
- administrative problems (e.g. patient's non-compliance)

In addition, the following conditions based on the Guidance on safety and ophthalmic monitoring should result in study drug discontinuation:

- Hepatic Increase in ALT > 5 x ULN Increase in AST > 5 x ULN
- New neurological symptoms accompanied by MRI findings unexpected for MS
- Diagnosis of macular edema

---

- Decrease in visual acuity with abnormal OCT (increase in central foveal thickness of > 20% compared to screening or cystic changes in the macula).

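### The protocol gives conflicting consequences for use of a prohibited medicine, cites sections that do not list these medicines, and has no rule for the biomarker samples taken afterwards

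*Protocol*

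**What the plan says.** Three parts of the protocol deal with a patient on fingolimod who receives a medicine that the study excludes.

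- **Protocol 5.4.8** lists immunosuppressants, immunoglobulins, monoclonal antibodies, interferon-beta, glatiramer acetate and ACTH as not allowed together with study drug. It adds: "use can only be considered if the study drug is permanently discontinued". The same section permits atropine, sympathomimetics and short-course methylprednisolone for stated purposes.
- **Protocol 5.4.5** gives conditions that may lead to an interruption. One is "emergency medical condition, unplanned hospitalization, involving use of excluded concomitant medications". On resuming it says: "Re-start decision should be made on a case by case basis and should be discussed with the Medical Advisor at Novartis". Restart also needs the sponsor's agreement.
- **Protocol 5.4.9** includes "use of prohibited medications, listed in Section 5.1 and 6.6.5" among events that "may be considered sufficient to support a decision about the study drug discontinuation in individual cases".

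On sampling, Protocol 5.4.6 delays the blood sample by at least 1 month after a corticosteroid course. No other on-study medicine has a sample-timing rule. At entry, Protocol 4.1 requires 1 month off interferon or glatiramer, and also states: "Last cyclophosphamide, mitoxantrone, teriflunamide, natalizumab and azathioprine dose of the patient should be at least 3 months before study entry".

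On analysis, Protocol 9.1 and SAP 6 take all MS patients and the control group as the analysis sets. SAP 6.5.1 (ELISA) and 6.5.2 (flow cytometry) compare Control with Visit 1, Visit 1 with Visits 2 and 3, and Control with Visit 3.

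**The concern.** A site with a patient who was given an excluded medicine in hospital finds permanent discontinuation as the condition in one section, a pause with possible restart in another, and investigator discretion in a third. The section on discontinuation sends the reader to the wrong place for the list. Protocol 1.1 itself warns that infection risk may rise when fingolimod is combined with other immunosuppressants, so the wording on combined exposure should not be open to conflicting readings.

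The statistical stake is narrower. The endpoints are cytokine and chemokine levels, and the excluded medicines act on the immune system. If such a patient is restarted, samples at the next visits reflect fingolimod plus the other agent, yet they enter the comparisons as on-fingolimod values. The same changes are the predictors in the secondary objective. Different readings at different sites would also make the mix of affected samples depend on the site.

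**Working it through.** The plan gives no figure on this point, so the check is mainly a comparison of texts.

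**1. Do the consequences differ?** Section 5.4.8 makes permanent discontinuation a precondition of use. Section 5.4.5 lists use of excluded medicines, within an emergency or unplanned hospitalisation, as a ground for interruption, and its restart text makes no exception for these patients and states no washout. Section 5.4.9 is permissive. It contrasts with a second list in the same section (liver enzymes, unexpected neurological findings, macular oedema, reduced visual acuity with abnormal OCT) that should lead to discontinuation. No sentence says which of the three sections prevails.

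**2. Where is the list?** Section 5.4.9 cites 5.1 and 6.6.5. Section 5.1.1 says "Treatment will be 0.5 mg p.o fingolimod daily for the treatment arm" and 5.1.2 says "No additional treatment beyond investigational treatment is requested for this trial". Section 6.6.5 is the heading for other biomarkers, marked not applicable. Neither lists a prohibited medicine. The list is in 5.4.8.

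**3. Would other rules remove the affected samples?**
- Section 6.3 treats a total of 1 month off study medication as withdrawal. A patient paused for less than that stays in.
- Section 5.4.9 lets patients who discontinue for a listed condition be considered withdrawn. The Glossary defines treatment discontinuation as a permanent stop, so a pause with restart is not clearly covered.
- Neither Protocol 9.1 nor SAP 6 excludes, censors or flags samples after a prohibited medicine, or says that withdrawn patients' data are dropped.

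The open route is therefore a patient restarted, with sponsor agreement, after less than 1 month off drug.

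**4. Which comparisons are touched?** Visit 1 vs 2, Visit 1 vs 3 and Control vs Visit 3, for ELISA and flow cytometry, and the changes used for the secondary objective. Control vs Visit 1 uses pre-treatment samples and is not touched.

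**5. Does the protocol recognise carry-over?** For some of the listed drugs, yes. Section 4.1 asks for 1 month off interferon and glatiramer, and 3 months off cyclophosphamide, mitoxantrone, natalizumab and azathioprine. It sets no interval for immunoglobulins, cyclosporine, methotrexate, cladribine, ACTH or monoclonal antibodies other than natalizumab.

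**6. How large could the effect be?** The documents give neither a rate of use nor an effect on cytokines, so this is illustration only. Inputs: 60 patients (the enrolment minimum), and a design difference of 7 pg/ml and SD of 15 pg/ml for IL-17, all from Protocol 9.8. Assumed: 2% to 5% affected, that is 0.02 × 60 = 1.2 to 0.05 × 60 = 3, or about 1 to 3 patients, each with an added shift of 7 to 15 pg/ml.

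Shift in mean change = (number affected × added shift) / 60.

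- 1 patient, 7 pg/ml: 1 × 7 / 60 = 0.12, or 1.7% of 7.
- 3 patients, 15 pg/ml: 3 × 15 / 60 = 0.75, or 10.7% of 7.
- 6 patients, 15 pg/ml, as a pessimistic case: 6 × 15 / 60 = 1.5, or 21.4% of 7.

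**The case against.** The best defence reads the sections as a rule plus the handling of breaches: 5.4.8 governs planned use, 5.4.5 covers an emergency in which an excluded drug has already been given, and 5.4.9 lists grounds that may justify stopping. That reading is reasonable, but no text states it. It would not mend the dead cross-reference or supply a rule for the later samples.

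Several parts of the defence stand:

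- A reader might infer that a site could simply continue fingolimod. No passage authorises that. The discretionary wording in 5.4.9 does not override the ban in 5.4.8.
- A reader might infer that restart is left to the site. It is not: 5.4.5 requires sponsor agreement and discussion with the sponsor's medical advisor, although it gives no criterion.
- A reader might infer that every prohibited medicine carries an entry washout that is then waived on study. Section 4.1 covers only some of them, and immunoglobulins, for example, have none.
- The absence of an on-study sampling delay is partly to be expected. Corticosteroids have one because they are permitted, while the other medicines are not meant to be combined with study drug. What is missing is a rule for handling deviations.
- The withdrawal provisions in 5.4.9 and 6.3 will take some of these patients out of the study.

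**Conclusion.** The point holds as an internal inconsistency with a modest effect on the analysis. Section 5.4.8's permanent stop does not agree with 5.4.5's possible restart or 5.4.9's discretion. The cross-reference in 5.4.9 leads to no list. Samples from a patient restarted after less than 1 month off drug stay in three of the four planned biomarker comparisons with no flag or sensitivity analysis.

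It would be tempting to conclude that the primary objective is compromised. The documents do not support that, because the Control vs Visit 1 comparison precedes any study treatment. Nor can the contamination be sized from the documents. The range of 0.12 to 0.75 pg/ml (1.5 in the pessimistic case) rests wholly on assumed rates and shifts, and the subset actually restarted may be smaller still. The reason to act is that the rules conflict on combined immune-modifying treatment and that the repair is cheap.

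**What to change.** 1. Amend Protocol 5.4.5, 5.4.8 and 5.4.9 so that they state one consistent consequence for use of a prohibited medicine. Which consequence is for the sponsor's medical team to decide.
2. In Protocol 5.4.9, replace the reference to Sections 5.1 and 6.6.5 with Section 5.4.8.
3. In SAP 6.5.1 and 6.5.2, flag every biomarker sample taken after the first on-study use of a medicine prohibited in 5.4.8. The flag should not capture the atropine, sympathomimetics or methylprednisolone that the same section permits. Repeat Visit 1 vs 2, Visit 1 vs 3 and Control vs Visit 3 without the flagged samples as a sensitivity analysis, and report how many samples were flagged.

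The cost is a wording amendment and one further run of tests already planned. The sponsor must also confirm that the CRF records the drug and its dates: Protocol 5.4.7 has patients notify the site of new medicines and 9.3 plans a summary, but Table 6-1 has no row for concomitant medication.

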#### **5.4.9 Discontinuation of study treatment and premature patient withdrawal**

Patients may voluntarily withdraw from the study for any reason at any time. They may be considered withdrawn if they state an intention to withdraw, fail to return for visits, or become lost to follow-up for any other reason.

If premature withdrawal occurs for any reason, the investigator must make every effort to determine the primary reason for a patient's premature withdrawal from the study and record this information on the Study Completion CRF.

The investigator should discontinue study treatment for a given patient or withdraw the patient from study if, on balance, he/she believes that continuation would be detrimental to the patient's well-being.

Study drug must be discontinued for a given patient if the investigator determines that continuing it would result in a significant risk for that patient. The following conditions/events may be considered sufficient to support a decision about the study drug discontinuation in individual cases:

- serious adverse event (e.g. cardiac failure, diagnosed malignancy)
- abnormal laboratory value(s) including liver function tests or abnormal test result(s) (e.g. PFTs, MRI and ophthalmic findings). See below and Appendix 7 and 8 for guidance for safety monitoring
- withdrawal of consent (e.g., in case the patient does not consent to continue in the study after a confirmed relapse or disability progression)
- pregnancy
- use of prohibited medications, listed in Section 5.1 and 6.6.5
- adverse events
- protocol violation
- unsatisfactory therapeutic effect
- patient's condition no longer requires study treatment
- administrative problems (e.g. patient's non-compliance)

In addition, the following conditions based on the Guidance on safety and ophthalmic monitoring should result in study drug discontinuation:

- Hepatic Increase in ALT > 5 x ULN Increase in AST > 5 x ULN
- New neurological symptoms accompanied by MRI findings unexpected for MS
- Diagnosis of macular edema

---

- Decrease in visual acuity with abnormal OCT (increase in central foveal thickness of > 20% compared to screening or cystic changes in the macula).

Patients who discontinue study drug should not be considered withdrawn from the study, unless one of the conditions listed above have been met. The sponsor should be notified about any decision regarding discontinuation of the study medication. Patients who discontinue the study drug should be treated according to the best standard of care. In addition to scheduled visits, patients who discontinue study drug due to adverse events or abnormalities on safety monitoring tests must be followed up with additional visits as needed in order to confirm the resolution of abnormalities. A Study Drug Discontinuation CRF should be completed, giving the date and primary reason for stopping the study drug.

For patients who are lost to follow-up (i.e. those patients whose status is unclear because they fail to appear for study visits without stating an intention to withdraw), the investigator should show "due diligence" by documenting in the source documents steps taken to contact the patient, e.g. dates of telephone calls, registered letters, etc.

Patients who are prematurely withdrawn from the study will be replaced by an equal number of newly enrolled patients.

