## **6.3 Treatment exposure and compliance**

In order to collect accurate information about the study drug exposure, the following records should be maintained for each patient: records of study medication dispensed and returned, dosages administered and intervals between visits.

Compliance will be assessed by the investigator and/or study personnel at each visit using capsule counts and information provided by the patient. A monitor will perform and document drug accountability during site visits and at the end of the study.

Patients who discontinue study medication for 1 month totally will be considered withdrawn.

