6 ANALYSIS PLAN

Data analysis will be performed after all of the data is collected from the enrolled patients. All MS patients and control group will be accepted as the analysis sets.

Cytokine and chemokine levels will be analyzed cumulatively at the end of the study. The results will be recorded to the blood sampling logs and laboratory logs cumulatively.

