6.5 ASSESSMENT OF CYTOKINE AND CHEMOKINE LEVELS

6.5.1 ELISA

Subjects' **IL-4, IL-6, IL-8, IL-9, IL-10, IL-13, IL-17, IL-23, IFN- γ , TNF- α , VLA4, CCL2, CCL5, CXCR3 and CXCL13** values will be tabulated by calculating mean and standart error and compared as Control group vs. Visit 1 (MS patients), Visit 1 (MS patients) vs. Visit 2 (MS patients), Visit 1 (MS patients) vs. Visit 3 (MS patients) and Control group vs. Visit 3 (MS patients) by using appropriate statistical test. Mann Whitney U test with significance level of 0.05 was used for the independent variables since non-normal distributions had been observed. Wilcoxon test was used for the dependent variables with non-normal distributions. For the independent variables with normal distributions Independent Sample t test was used whereas Paired sample t test was used for the dependent variables with normal distributions.

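### On-treatment change is tested only in patients with complete pairs, withdrawals are replaced but never analysed, and the Visit 3 results are exposed if loss is linked to response

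*Protocol*

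**What the plan says.** **Replacement.** Protocol section 5.4.9: "Patients who are prematurely withdrawn from the study will be replaced by an equal number of newly enrolled patients".

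**Tests of change.** SAP sections 6.5.1 (ELISA) and 6.5.2 (flow cytometry) compare Visit 1 with Visit 2 and Visit 1 with Visit 3 separately. A Wilcoxon test is used for non-normal data; otherwise "Paired sample t test was used for the dependent variables with normal distributions". SAP section 6.4 treats the clinical scales in the same way, for Visit 1 versus Visit 3 only. Both ELISA and flow cytometry values are also compared between controls and MS patients at Visit 1 and at Visit 3.

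**Analysis set.** SAP section 6: "All MS patients and control group will be accepted as the analysis sets". Protocol section 9.1 agrees. Neither document says how withdrawn patients and their replacements are counted.

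**Reasons for stopping.** The protocol's list in section 5.4.9 includes adverse events, withdrawal of consent (with relapse or progression as the example) and "unsatisfactory therapeutic effect". The investigator must find the primary reason for withdrawal and "record this information on the Study Completion CRF".

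**Who counts as withdrawn.** Section 5.4.9: "Patients who discontinue study drug should not be considered withdrawn from the study, unless one of the conditions listed above have been met". Section 6.3: "Patients who discontinue study medication for 1 month totally will be considered withdrawn".

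**What is absent.** Neither document contains a missing-data rule, a joint model over visits, a sensitivity analysis, a disposition table or a comparison of completers with patients who left.

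**The concern.** A paired test can use only patients who have both values. The Visit 1 versus Visit 3 test is therefore a completer analysis, whatever the analysis set is called. A patient who gives samples at Visits 1 and 2 and then leaves contributes nothing to it, although the Visit 2 value says something about where that patient was heading. The Visit 1 versus Visit 2 test does keep that patient, so the two tests can rest on different people.

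Replacement adds to this. The number of pairs can return to its target while the patients who left stay outside the result, and no planned table shows how many there were or how they differed.

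At stake is the question that Protocol section 1.2 calls the main purpose: whether fingolimod shifts the cytokine balance. If patients who respond less leave more often, the completer change overstates that shift. Control versus Visit 3 depends on the same selected patients.

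**Working it through.** **1. The plan's own figures.** Protocol section 9.8 and SAP section 5.1 give a difference of 7 pg/ml in matched pairs, SD 15, power 90%, type I error 0.05, 50 pairs, 20% drop-out and 60 patients.

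- Pairs: n = (15 × (1.960 + 1.282) / 7)² = 48.2, so 49. The noncentral paired t gives 89.9% power at 50 pairs. The stated 50 is reproduced (two-sided).
- Enrolment: 50 × 1.20 = 60, as stated. Dividing by the retained fraction gives 50 / 0.80 = 62.5, so 63. With 60 enrolled and 20% lost, 48 pairs remain and power is 88.6%.

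The loss of power is small. The question is who the remaining pairs are.

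**2. How many patients could lie outside the Visit 3 test.** Suppose replacement continues until 60 patients complete and replacements leave at the same rate d. Patients treated = 60 / (1 - d).

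| d | Treated | No Visit 1-Visit 3 pair |
|---|---|---|
| 10% | 67 | 7 |
| 20% | 75 | 15 |
| 30% | 86 | 26 |

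The target of 60 completers is an assumption. The documents do not say whether 60 or 80 refers to enrolled or completing patients.

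**3. Simple bound.** Overstatement = d × (mean change in those who leave - mean change in completers). Let completers change by -7. At d = 20%:

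- leavers would have changed by -3.5: 0.20 × 3.5 = 0.7 pg/ml;
- by 0: 0.20 × 7 = 1.4 pg/ml;
- by +7: 0.20 × 14 = 2.8 pg/ml.

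If leavers would also have changed by -7, the overstatement is 0.

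**4. Completers versus a likelihood estimate.** Simulation inputs: 60 patients, SD 15 at each visit, true change -7 at Visits 2 and 3, 20% lost, correlation between visits 0.3 to 0.7. The log-odds of loss rise by 0.02 to 0.10 per pg/ml of poorer Visit 2 change. Only 7, 15 and 20% come from the documents. There, 7 is stated for matched pairs and 15 for basal IL-17, so applying them to on-treatment change is itself an assumption.

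Strength of selection: the SD of change is 15 × √(2(1 - ρ)), which is 17.7 at ρ = 0.3 and 11.6 at ρ = 0.7. A slope of 0.02 is then an odds ratio per SD of exp(0.02 × 11.6) = 1.26 to exp(0.02 × 17.7) = 1.43. A slope of 0.10 is exp(1.16) = 3.2 to exp(1.77) = 5.9.

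| Estimate of Visit 3 change (truth -7) | Loss after Visit 2 | Loss before Visit 2 |
|---|---|---|
| Paired completers | -7.3 to -9.2 | -7.3 to -9.2 |
| Likelihood, all with Visit 1 | -7.0 to -7.1 | -7.2 to -7.9 |

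Completer bias is 0.3 to 2.2 pg/ml, or 0.3/7 = 4% to 2.2/7 = 31% of the assumed change. The standard error of the likelihood estimate is about the same or slightly lower (for example 2.11 against 2.14).

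**5. What replacement does.** Take a true mean change of 0, SD of change 15, 20% loss that depends on the unseen change itself, and a nominal two-sided 5% test.

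| Odds ratio of loss per SD of worse change | Completer bias (pg/ml) | Rejection, 48 completers | Rejection, refilled to 60 |
|---|---|---|---|
| 1 (unrelated) | about 0 | 5.1% | 5.0% |
| 1.65 | -1.4 | 10% | 12% |
| 2.7 | -2.6 | 23% | 29% |
| 7.4 | -3.9 | 53% | 63% |

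Refilling leaves the bias unchanged and only adds precision around it. If loss is unrelated to change, replacement does no harm to the test.

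**The case against.** **The main result is not at risk.** The stated primary objective compares controls with MS patients. Control versus Visit 1 uses samples taken before any drop-out, and Protocol section 9.5 plans no specific hypothesis. This stands.

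**Replacement is not the cause.** A reader might infer that replacing patients turns the fingolimod analysis into one of completers only. It does not: testing by pairs does that, with or without replacement, and only for Visit 1 versus Visit 3. Visit 1 versus Visit 2 uses all available pairs. This stands.

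**Drop-out is not concealed.** Reasons for withdrawal and for stopping drug go on CRFs, subject numbers are not reused, and the analysis set does not exclude withdrawn patients. This stands too. The gap is that no analysis or table of withdrawals is planned, not that the data are missing.

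**Outcome-related loss is not shown.** Unsatisfactory effect is one item in a list of conditions that may support stopping the drug, and section 5.4.9 separates stopping drug from withdrawal. Under the plan cytokines are analysed at the end of the study, so Visit 2 values could not guide a decision. Any link must run through clinical response, and whether cytokine change and clinical course are related is what the secondary objective sets out to test. This limits the claim to a possibility. It does not remove it: the separation in section 5.4.9 has an exception for the listed conditions, unsatisfactory effect is one of them, and section 6.3 counts a month off drug as withdrawal.

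**The size follows from the assumptions.** With weaker selection (slopes 0.01 to 0.02) the completer bias is only about 0.1 to 0.6 pg/ml, against a standard error of 1.6 to 2.7. The likelihood estimate is nearly unbiased when loss follows Visit 2 because loss was made to depend on observed values. The simulation also used normal raw-scale data, whereas the SAP reports non-normal distributions. All of this is fair and is reflected in the verdict.

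**Conclusion.** The point holds in a limited form. The planned Visit 1 versus Visit 3 tests use only patients with both samples, which does not match an analysis set of all MS patients. They leave unused the Visit 2 values of those who leave later. One-for-one replacement restores the count but not the missing outcomes, and nothing planned would show the reader the difference.

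Visit 1 versus 3 and Control versus Visit 3 are exposed; the primary comparison at Visit 1 is not. Under the assumptions of working step 4, completer bias is about 0.3 to 2.2 pg/ml. The correlation, the strength of selection, and the timing and mechanism of loss are not in the documents, so neither the direction nor the size of any real bias can be known from them.

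Two stronger readings should be avoided. The documents do not show that loss will be related to response; they only list reasons that could make it so. Nor does a likelihood model cure the problem in general: it removes nearly all of the simulated bias if loss follows Visit 2, only part if loss precedes it, and cannot correct for loss that depends on values nobody observed. This is a worthwhile, cheap improvement and not a flaw that invalidates the study.

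**What to change.** **Model.** For each marker, fit one likelihood-based repeated-measures model with visit as a factor and unstructured covariance. Use a log or other suitable scale, with a stated rule for undetectable values. Include all MS patients with a Visit 1 sample, also those later replaced, and report Visit 1 versus 2 and Visit 1 versus 3 from it.

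**Sensitivity.** Keep the planned paired or rank tests as completer sensitivity analyses. Add a delta-adjusted analysis for loss that depends on unseen values.

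**Reporting.** Tabulate numbers withdrawn and replaced by visit and reason, with Visit 1 and Visit 2 values by completion status.

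**Reconcile.** Protocol sections 5.4.9 and 6.3 must agree on who counts as withdrawn, because that decides who is replaced.

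**Cost.** SAP text, a consistent protocol definition of withdrawal, and slightly more analysis. No new samples or CRF data are needed. The downside is a modelling assumption about scale, which the retained rank tests help to check.
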